9. RISKS TO INTERVENTION SUBJECTS

The overall risks to participants for this study are expected to be minimal. In our feasibility study, no adverse effects were reported. The risks associated in the participant characteristics or study procedures include: (1) concern about suicide; (2) MRI; (3) tDCS; (4) blood draw.

Concern and protection about suicide and harm to others:

The assessment of suicidality or need for hospitalization will be based on following assessments throughout the study period: (1) responses to the C-SSRS at baseline and follow-up assessments. The C-SSRS assesses past and current risk of suicide and suicidal ideation. All coordinators in this study have been certified to administer this measure and obtain a risk score based on intervention subject responses. (2) GDS combined with P4 is assessed weekly during an in-person tDCS session, and follow-up assessment visits. GDS, specifically, responding 'No' to GDS item 11 – "It is wonderful to be alive now" will be followed immediately by the P4 suicidality screener, and by mental status examination of the participant. (3) the partner subject's response to the Depression/Dysphoria item #7 on the NPI. In the event that a suicidality risk is detected by the NPI, we will ask the partner subject about the risk of the intervention subject for hurting himself/herself, and administer to the P4 suicidality screener to the intervention subject within 24 hours. Across all three scenarios, the research staff will assess for severe hopelessness, passive death wish, suicidal statements, suicidal plan, or behavioral indicators of risk for self-harm. Need for hospitalization will be similarly assessed by a study physician. Hospitalization is typically indicated if there is imminent risk of harm due to agitation, such as refusal to eat, weight loss, violent behavior toward the caregiver, or suicidality. We have established a standard protocol for addressing concern on suicide patients at risk or with dementia, by working with certified geriatric psychiatrist or neurologist from our Memory Clinics (including [name], co-I of the study and a geriatric psychiatrist working at the clinic). The clinician will provide immediate care to any participants at risk of suicide or clinically unstable. If a participant is

judged to be at immediate high risk and leaves study venue against the advice, we will contact security or other appropriate emergency personnel (e.g., ambulance, mobile crisis team).

For the partner subject's response to the Agitation/aggression item #7 on the NPI, we have procedure in place for training staff's home visit to address the potential harm. If the staff detects an imminent risk of harm to the subject or others, the staff will call 911. Otherwise, the study team's geriatric psychiatrist and the PI will be contacted.

Risk and Protection against Risk Related to MRI Imaging Assessments:

There is no immediate risk from exposure to magnetic fields of 3 Tesla. Possible anxiety may result from claustrophobia or dizziness experienced by the intervention subjects when placed in the magnet. During the imaging portion of the experiment, intervention subjects must remain in the bore of the magnet, which is approximately 3 feet in diameter. Also, the scanning coil closely encloses the intervention subject's anatomy being imaged. These two factors may increase the likelihood of claustrophobia. Should the intervention subject feel discomfort, the experiment will be terminated upon their request.

In rare cases, contact with the MRI transmitting and receiving coil or conductive materials such as wires, or skin-to-skin contact that forms conductive loops, may result in excessive heating and burns during the experiment. The operators of the MRI scanner will take steps, such as using foam pads when necessary, to minimize these risks. The intervention subjects will be informed of the risk and instructed to immediately report any heating sensations. In the rare event that this would occur the experiment will be terminated and, if necessary, we will have the intervention subject seek medical treatment.

Intervention subjects will be screened for magnetic material before each study. Intervention subjects with pacemakers, aneurysm clips (metal clips on the wall of large artery), metallic prostheses (including heart valves and cochlear implants) or shrapnel fragments are at risk in an MR environment. Welders and metal workers are also at risk for injury because of possible small metal fragments in their eyes. Those at risk will be excluded from the study.

The effect of exposure to MRI scanning on an unborn child is unknown. Exposure to MRI scanning might be harmful to a pregnant female or an unborn child. There are no established risks at this time, but the intervention subjects will be informed that there is a possibility of a yet undiscovered pregnancy related risk.

MRI scanning produces a loud tone that can cause damage to the inner ear if appropriate protection is not used. Adequate protections in the form of earplugs or close-fitting silicon-padded headphones will be provided.

We cannot guarantee direct benefits from participating in the MRI assessment. fMRI are unique techniques in their ability to non-invasively study human brain function.

Discovery of Previously Unknown Conditions (conditions that can be diagnosed from having access to research-quality MRI):

Our scans are not read by a neuroradiologist, and the intervention subjects are explicitly told that the experiment will not provide information regarding their health status. However, if the certified MRI technician suspects something abnormal, he/she will seek advice from a qualified neuroradiologist, and the subject will be notified that his/her MRI indicated a potentially abnormal finding. With the subject's permission we will send information to their physician.

If a participant withdraws from the study, all attempts will be made to collect data to allow for inclusion in the analysis. Reasons for withdrawal will be recorded.

Risk and Protection against Risk related to tDCS Conditions:

The protocol described here uses stimulation levels that fall well within established safety limits. More than 500 research studies involving thousands of subjects have been published using tDCS (source: PubMed). A number of researchers have addressed the safety of tDCS. They have all concluded that tDCS is a painless technique for safely modulating cortical excitability. No serious or long-lasting effects have been reported. A recent meta-analysis of 209 studies found no serious adverse effects. The same meta-analysis found frequent mild adverse effects, such as itching and tingling⁴⁹. All of these effects were transient and were localized to the skin at the stimulation site. A more focused study with 131 subjects undergoing 277 tDCS sessions reported similar findings: no serious adverse effects, but frequent mild effects, including itching and tingling⁵⁰. The most common mild, localized, and transient adverse effects are, in order of decreasing frequency: itching, tingling, mild headache and burning sensation. Most people do not find these sensations to be painful. Skin redness in the area of stimulation is often reported. Itching, tingling and burning usually occur at the beginning of stimulation while the current is ramped up. These sensations are reduced by gradual current ramping (as it will be done in this study). Finally, some subjects report that these sensations are uncomfortable as some individual characteristics such as type of skin and hair might result in a higher stimulation of the skin nerve receptors. tDCS has only short lived, mild effects on brain activity. To ensure safe use of the tDCS device, the device will be carefully inspected before each use. The batteries will be removed after each use to prevent corrosion that could occur after long periods of non-use. The device will be stored in a dry location. Of note, in our pilot study of older subjects (reported in the “preliminary studies” section), there have been no adverse events.

We will provide training of the stimulation to our experienced project coordinators. The training will be provided by co-I [name], who is an expert in tDCS, and [name] (an experienced tDCS coordinator working on our feasibility study). Evaluation will be conducted by investigator team before a project coordinator can independently work on it.

The interventionists will ask every intervention subject’s study partner subject to complete the NPI-Q weekly during the intervention period to monitor changes in NPS among the intervention subjects during the 4-week tDCS sessions. If any symptoms worsen over the intervention period and a worsening is confirmed by the study partner subject, it will be reported as an adverse event (in accordance with reporting procedures described in Section 16). The intervention will then be discontinued. Our co-I, [name], who is a geriatric psychiatrist, will be notified and provide medical assessment and further advice for medical assistance.

Device-Specific Risk Minimization:

Soterix Medical outlines the same risks and risk control features for both devices, tES Model 2001 and tDCS Model 1300A, as follows:

Irritation

- The applied current may cause minor irritation, discomfort, and/or redness at the electrode sites.
- Soterix Medical *EASYPad*™ electrodes should not be placed over previously irritated, burnt, or damaged skin.

Methods of Risk Minimization:

- **SMARTscan™**: a visual 20 bar LED display (1 to 20 from left to right) that indicates to the

operator the contact conditions of the electrodes before, during, and after stimulation. LED 1 denotes short condition and LED 2 denotes open-circuit condition. Stimulation should not begin if either LED 1 or LED 2 is lit.

- **PRE-STIM TICKLE:** a pre-stimulation feature that conditions the skin prior to full stimulation,
- **RELAX:** a feature that allows the operator to decrease the set level of current from the maximum (FULL CURRENT) value to accommodate subject feedback at any point without aborting the stimulation session.
- **TRUE CURRENT™** display is active whenever the device is on and indicates the actual value of current (in mA) being supplied from the device to the electrodes, regardless of device settings. This feature functions as a fully independent and redundant safety feature when monitored by the operator.

- **Stimulation ABORT:** this feature allows the operator to terminate the stimulation at any point by pressing the ABORT button, which *will ramp down the current to zero in 30 seconds and terminate the entire stimulation run. Of note, too rapid ramp down (< 10 seconds) are not recommended.* Aborting the stimulation run is recommended if the TRUE CURRENT™ display deviates from expected output current, the TIME REMAINING display deviates from expected duration setting, intervention subject complaints any unusual adverse effects (i.e., beyond itching, tingling, mild headache, and mild burning sensation), and/or request to stop. In the event that the stimulation is terminated, the device will not be re-started and the session will be considered complete.

Risk and Protection against Risk Related to Blood Collection:

We will explain to intervention subjects the potential risks from venous blood collection, which include pain, a bruise at the point where the blood is taken, redness and swelling of the vein, infection, and a rare risk of fainting. We will utilize trained CRC staff to implement the following strategies to reduce the potential risks associated with venous blood collection and to protect research intervention subjects. To reduce pain, the CRC staff will use a needle of smaller gauge than the selected vein. To prevent bruising, CRC staff will insert the needle into the selected vein at an angle of 30 degrees or less. In addition, the use of a needle of smaller gauge helps prevent bruising. For the rare risk of fainting, intervention subjects will be asked to lie down if they express concern. Snacks will be provided to intervention subjects after each blood collection.

Other Procedure-related Considerations for Protection Against Risks

Informed Consent: At the screening stage, we ask the intervention subject for verbal consent for phone screening. If eligible to continue with step 2 of screening, decision-making capacity will be assessed using San Diego Brief Assessment of Capacity to Consent (UBACC) to ensure older adults who attend the proposed study have adequate capacity for giving consent and making decisions prior to enrollment (see section 7 for informed consent details).

Additionally, intervention subjects who lack capacity to consent may become emotionally distressed by that determination. However, intervention subjects will be reminded that this determination is merely meant to ensure their continued safety and understanding of the research study only, and does not indicate any impairment in their daily lives (see additional protections against risks for more details).

Psychological Distress: Although the questions asked of the intervention subjects and study partner subjects involved in the study have been regularly used in RCTs, the challenges from answering questions about another person, or knowing a study partner subject will be asked to answer questions about the intervention subject themselves, may produce frustration or anxiety. The PI will work closely with the research staff and intervention subjects/study partner subjects to help alleviate any concerns.

Confidentiality and Privacy:

Intervention subject data will be collected with the verbal and/or written consent of the intervention subject and study partner subject. Information pertaining to individual participants will be released with the participant's permission only. All participant data will be identified by a uniquely coded screening ID assigned to each respondent and study ID for participants eligible for enrollment. Access to the master

links between name and screening ID, as well as between screening ID and study ID, will be restricted to the study team.

All hard-copy based materials and data will be kept in a locked research office in a locked file cabinet. No one other than the study team will have access to the data. Once data have been entered into a REDCap Consortium (Research Electronic Data Capture), only code numbers (not names) will be associated with individuals' research data records. REDCap is a free, secure, HIPAA-compliant, web-based application used for electronic management of research study data, which can then be downloaded into SPSS for data analysis. REDCap servers are housed at the University of Rochester and all web-based information transmission is encrypted. Data from the REDCap database will be directly downloaded to a password-protected UR-SON server for access by the PI and study team. A list of names, home addresses, email (optional), telephone numbers of study participants will be used only for study purpose, and study management software (Filemaker Pro) will be used by the study team only, in a secure manner on UR-SON servers. All School of Nursing servers are routinely audited for vulnerabilities or improper configurations by the University of Rochester's Information Security team using the Nessus scanner, which is an industry leader in security assessment.

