4. STUDY DESIGN

This is a Stage 0 study for mechanistic understanding. We will recruit older adults with study partner-rated NPS that has worsened in the past 2 years. Our previous study shows that this will capture

the most detrimental type of NPS.¹ We will focus on the MCI group, since understanding and modifying NPS among this group may assist in slowing the progression of dementia. See Table 1 for the overview of assessment and intervention timeline.

- Double-blind randomized controlled trial of 40 participants and their study partner subjects; all eligible and interested intervention subjects will be enrolled and undergo a baseline assessment, MRI scan, and blood draw; PI, staff conducting follow-up assessments and intervention subjects and their study partner subjects will be blinded. Interventionists and data managers will know randomization.
- After baseline, all intervention subjects will be randomly assigned to one of two groups - active anodal or sham C3 tDCS. A MATLAB block-based randomization code will be used to randomly assign study ID to group. Each study ID-group pairing will be printed and placed inside a sealed envelope labeled with only the study ID to ensure blinding. After an intervention subject and their partner subject finish baseline assessments, the interventionist or data manager will open the randomization envelope to assign the respective study ID.
- All intervention subjects will undergo a total of fourteen (14) 20-minute tDCS sessions over the course of four weeks: ideally, five times a week for two weeks, followed by twice a week for an additional two weeks. However, we will extend the intervention for additional two weeks for make-up sessions.
- Assessments will occur at baseline, within 2-week after finishing intervention (post-intervention assessment), and 4 to 6 weeks after post-intervention assessment (follow-up assessment).
- Unblinding will occur upon the completion of the follow-up assessment. We will not provide those in the sham group with the active tDCS procedure.

Primary endpoints:

- Resting-state and visual attention task-related fMRI;⁴⁵

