- Study sponsor, investigator, and all other study team members comply with the prohibitions outlined in 21 CFR §812.7 prohibiting promotion and other practices.

4.2.1 Device Storage & Control & Accounting: The 1x1 tES device will be stored in a locked cabinet, with all of its original contents and appropriate labelling (as in accordance with 21 CFR §812.5). Only the investigator and project coordinator will have access to this locked device. Along with the device and its components, records for when the device was received by the manufacturer, when and on whom the device was used, who administered the device to the intervention subject, as well as up-to-date staff training and procedural logs will all be maintained by the investigator and project coordinator. Furthermore, all safety precautions regarding storage and usage of device outlined in the manufacturer's manual will be followed and records for compliance with storage, handling, and maintenance will be documented.

We will provide training of the stimulation to our experienced project coordinators prior to their administration of the device on intervention subjects. The training will be provided by co-I [name] who is an expert in tDCS and [name] (an experienced tDCS coordinator working on our feasibility study). Evaluation will be conducted by investigator team before a project coordinator can independently work on it.

4.2.2 Intervention Procedures:

For all 40 intervention subjects, tDCS (LPG/C3-anode, orbitofrontal cortex/Fp2-cathode) or a sham intervention will be administered for 4 weeks (1 session per weekday for 2 weeks, and then 2 sessions per week for 2 weeks, for a total of 14 sessions).

If any sessions are missed, make-up sessions will be provided, and the length of intervention period will be extended to ensure everyone receives a total of 14 sessions. Intervention subjects can choose to have the tDCS sessions where they feel comfortable (e.g., CogT Lab or their home). The maximum window for make-up sessions is two weeks.

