Assessments: Fully eligible participants and their study partner subjects will be notified of their eligibility for the study. Baseline assessments need to be scheduled within one month of in-person cognitive screening. Participants will then be asked to complete baseline measures (assessment, MRI scan, and blood draw), after which they will be randomized to either the active or sham tDCS intervention condition. The blood draw may occur within 2 weeks (before or after) the baseline assessment and MRI scan. The beginning of the intervention phase will start within two weeks after the baseline assessment and blood draw. Follow-up cognitive assessments and MRI scans for each participant will occur within 2 weeks after completion of intervention (i.e., post-intervention assessment) and then 4 weeks after post-intervention assessment (i.e., follow-up assessment). We will allow 2 weeks to make up the follow-up assessment. At the same time points, study partner subjects will be administered the NPI, AES, and QOLAD. Follow-up assessments for study partners can also be conducted over the phone, at the partners discretion.

A detailed overview of data collection measures for screening and assessments can be found below in **Table 1**. To reduce the burden on participants, study partner subjects, and staff, as well as to avoid practice effects of cognitive measures, for individuals who are eligible for the study, their screening data will be used as baseline data; for those who are not eligible for the study, their screening data will only be used for summarizing the reasons for ineligibility.

Group assignment/randomization will be determined with a block-based matlab randomization.

Table 1: Study Measures I = intervention subject; P = partner subject

	Screening		Baseline	Interventions				Makeup Interventions (if needed)		Post-Intervention Assessments	
	Phone	In-Person		Week 1	Week 2	Week 3	Week 4	Week 5	Week 6	Immediate Post-Intervention	Final Post-Intervention
Study Activities											
Verbal Consent for Screening	I, P										
Inclusion/Exclusion (verified at In-Person)	I, P	I, P									
MRI Screening Form	I										
Informed Consent		I, P									
UBACC		I									
Demographics & background		I, P									
MoCA (V2)		I									
RAVLT		I (Lists C&D)								I (Lists A&B)	I (Lists C&D)
ADL-PI-self		I								I	I
PSS		I								I	I
PSQI		I								I	I
MFI		I								I	I
GDS-15		I		I	I	I	I	I	I		
AES		I, P								I, P	I, P
QoL-AD		I, P								I, P	I, P

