Medications		I									
Medication changes										I	I
NPI-Q	P			P	P	P	P				
NPI (Full)		P								P	P
Examiner			I (Form A)							I (Form B)	I (Form C)
GDS-30		I								I	I
C-SSRS		I								I	I
STAI		I								I	I
BVMT-R		I (Form 1)								I (Form 2)	I (Form 3)
DOSPERT		I								I	I
CRASH		I									
Blood Draw with questionnaire		I									
MRI scan (& confirm MRI screen form)		I								I	I
Intervention (sham or active)			I	I - One session per each weekday	I - Two sessions per week		I - Makeup sessions (if needed)				
MATLAB computer task				I - During each intervention session							
SAM				I - Before and after each intervention session							
Fatigue scale				I - Before and after each intervention session							

Note: For further details regarding measures, please see **Section 4: Study Design**.

Blood collection and processing:

We will collect a single blood sample from each participant within 2 weeks of the baseline assessment (before or after), and prior to beginning tDCS intervention sessions. This blood collection visit will require a separate appointment from the baseline assessment and MRI scan. Study staff will schedule the blood collection with CRC staff and confirm the appointment with the participant. Participants will be reminded to fast for 8 hours prior to their blood draw but may drink water and should take all medications as prescribed. On the day of the blood collection appointment, study staff will meet the participant at CRC and CRC staff will collect blood following a venous-blood collection protocol. Study staff will also ask each intervention subject 3-questions related to their diet and health in the past week. A total of 20mL of blood will be collected – 12mL into two 6mL plasma (EDTA-treated) tubes, and 8mL into two 4mL BD red serum tubes. Blood will be processed and frozen in cryo-vials at CRC -80° F freezer. Once cryo boxes are full (due to lack of space for storage of multiple cryo-boxes in CRC) then cryo boxes will be transferred to 4W-156, bio-safety level lab 2 in School of Nursing for storage in -80° F freezer until analysis.

No individual research results will be provided to intervention subjects or study partner subjects in this study. However, aggregate group results will be disseminated to all subjects after study completion.

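### The weekly partner NPI-Q is scheduled for weeks 1–4 only, although make-up stimulation can run through week 6, so worsening in weeks 5–6 may be found too late to stop treatment

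*Combined protocol and SAP*

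**What the plan says.** Section 9 (tDCS risks) has interventionists ask each study partner "to complete the NPI-Q weekly during the intervention period to monitor changes in NPS among the intervention subjects during the 4-week tDCS sessions". The rule that follows begins "If any symptoms worsen over the intervention period and a worsening is confirmed by the study partner subject": such worsening is reported as an adverse event, the intervention is discontinued, and the study's geriatric psychiatrist is notified.

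The planned course is 14 sessions in four weeks, but it can be lengthened. Section 4 states that "we will extend the intervention for additional two weeks for make-up sessions". Section 4.2.2 adds that "the length of intervention period will be extended to ensure everyone receives a total of 14 sessions" and sets the limit: "The maximum window for make-up sessions is two weeks".

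Table 1 (Section 8) has columns for make-up weeks 5 and 6 and lists make-up stimulation there. Its NPI-Q row is marked for the partner at phone screening and in weeks 1, 2, 3 and 4, and is blank afterwards. Its GDS-15 row is marked for the participant in each of weeks 1 to 6.

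After treatment, Section 8 says "Follow-up cognitive assessments and MRI scans for each participant will occur within 2 weeks after completion of intervention", and "At the same time points, study partner subjects will be administered the NPI, AES, and QOLAD". Section 12 pays the partner $10 per rating for four intervention weeks and two later assessments, up to $60.

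**The concern.** The weekly NPI-Q is the scheduled means by which the discontinuation rule learns of worsening. If it stops at week 4 while stimulation continues, the rule loses its scheduled input during the remaining sessions. The participants were enrolled because their partner-rated symptoms had already worsened over the past two years, so further worsening is a relevant event.

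A partner may not volunteer a report without being asked. The eligibility criteria require contact only about weekly, and attendance at only some of the study visits. Worsening that begins in week 5 or 6 could therefore first be recorded at the post-intervention NPI, when no stimulation is left to stop.

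**Working it through.** **Inputs**

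- Planned sessions: five per week for 2 weeks, then two per week for 2 weeks (Sections 4 and 4.2.2).
- Make-up window: at most 2 weeks (Section 4.2.2).
- NPI-Q and GDS-15 rows: Table 1, Section 8.
- Partner payment: $10 per rating, maximum $60 (Section 12).
- Post-intervention assessment: up to 2 weeks after the intervention ends (Section 8).

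**Plan's own figures**

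- Sessions: 5 × 2 + 2 × 2 = 14, as stated.
- Partner payment: (4 weekly + 1 post-intervention + 1 follow-up) × $10 = 6 × $10 = $60, as stated. A paid week-5 or week-6 rating does not fit within this total.

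**Reading Table 1**

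Both rows were laid against the 11 column headings (phone, in-person, baseline, weeks 1–6, two post-intervention visits).

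| Row | Weeks 1–4 | Weeks 5–6 | Post-intervention visits |
|---|---|---|---|
| Stimulation | planned | make-ups if needed | none |
| GDS-15 (participant) | marked | marked | blank |
| NPI-Q (partner) | marked | blank | blank |
| Full NPI (partner) | blank | blank | marked |

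The NPI-Q and GDS-15 rows each carry all 11 columns, so the blank NPI-Q cells do not look like damage from text extraction.

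**Size of the gap**

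- Scheduled partner ratings: 4 in weeks 1–4 and 0 in weeks 5–6.
- Calendar weeks uncovered: at most 2 of 4 + 2 = 6, reached only if make-ups run through both extra weeks.
- Interval between partner ratings: 2 make-up weeks + up to 2 weeks to the post-intervention visit = up to 4 weeks, against 1 week in the planned course. This assumes the week-4 NPI-Q is taken at the end of week 4. Stimulation can occur during the first 2 of those weeks.
- Share of the fixed 14 sessions falling in uncovered weeks: one make-up is 1/14 = 7%. The documents set no weekly cap on make-ups, so the other cases are assumptions: two per week for both weeks is 4/14 = 29%; one per weekday for both weeks is 10/14 = 71%.

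**With the NPI-Q extended**

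(6 weekly + 2 later assessments) × $10 = 8 × $10 = $80.

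**The case against.** The strongest reply is that Section 9 already covers the make-up weeks. It calls for weekly ratings throughout the intervention period, and Section 4.2.2 says that period is lengthened for make-ups. On this view four weeks is only the programme's nominal label, used elsewhere in the protocol, and Table 1 lags behind the text. The reading is possible, but it makes the table wrong, and the table is what staff will work from. On the narrower reading, stimulation continues without its scheduled check. A correction is needed either way.

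Second, payment does not define the schedule, because the partner's screening NPI-Q and NPI are also unpaid. That is fair: the payment agrees with the narrow reading but does not prove it.

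Third, the discontinuation rule is not confined to weeks with an NPI-Q. Staff who notice worsening in week 5 can ask the partner and stop. GDS-15 with the P4 screener, the SAM and fatigue ratings at each session, and the presence of a trained team member all continue. This stands, and it lowers the risk. But the SAM, fatigue and GDS-15 ratings come from the participant, and the P4 pathway is about suicidality, whereas the rule covers any symptom. Interventionists also know the allocation, while partners are blinded, so informal staff observation is not an equal substitute.

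Fourth, the largest figures need extreme cases: 71% requires 10 of the 14 sessions to be missed in weeks 1–4, and the 4-week interval requires both windows to be used in full. These are upper bounds, not expectations. Whether a brief worsening would still be picked up at the post-intervention NPI depends on that instrument's recall period, which the documents do not state.

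**Conclusion.** The concern holds. Table 1 leaves up to two weeks of permitted stimulation without the partner rating that supports the stopping rule, and the next scheduled rating falls after the last session. It rests on Table 1 as printed and on staff working from it.

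The effect is limited to participants who need make-ups, a number the documents do not give, and make-ups move sessions within the fixed 14 without adding any. The protocol describes the overall risk as minimal. This is a participant-safety gap that is cheap to close, and it has no bearing on the primary fMRI endpoints, power or alpha.

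**What to change.** 1. In Table 1, mark the NPI-Q for the partner in weeks 5 and 6, with a note that it applies to any week in which a make-up session is given.
2. In Section 9, replace the reference to four weeks of sessions with wording that covers every week with stimulation, make-up weeks included.
3. In Section 12, raise the partner maximum from $60 to up to $80, paying for each weekly rating actually completed.

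The discontinuation rule itself can stay as written. The cost is at most two short questionnaires and $20 per affected partner, plus the wording changes.
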